### 7.4 Blinding

The trial design is a single blinded trial. The trial participants will be blinded to their treatment.

Staff present at the time of operation, and prophylaxis, will be unblinded.

Health care staff not present at the time of operation will be blinded to treatment.

Outcome assessors will be blinded to treatment.

Final unblinding of all trial participants will occur after the creation of a locked analysis data set.

Medical/Anaesthetic notes will not contain the patient's treatment arm to limit unblinding.

Blinding of all care providers is not possible because of logistics relating to the blinding of treatments at short notice for all trial participants e.g. emergency surgery participants.

### 7.5 Unblinding

The study code will only be broken for valid medical or safety reasons e.g. in the case of a severe adverse event where it is necessary for the investigator or treating health care professional to know which treatment the patient is receiving before the participant can be treated. Subject always to clinical need, where possible, members of the research team will remain blinded. Documentation of the blinding arm will remain in the patient's notes to allow access as needed. If this information is accessed the person accessing the arm will be notified to inform the principal investigator. The PI will notify the study sponsor and relevant authorities.

## 7.6 Baseline data

Data collection includes but is not limited to:

### Pre-operative data

- Age
- Sex
- Height/Weight
- Co-morbidities
- Indication for surgery
- Pre-operative blood tests e.g. haemoglobin
- National Nosocomial Infection Score
- MRSA colonisation status
- Infection status. Defined by NNIS definitions
- Pre-operative radiotherapy
- Pre-operative chemotherapy
- Pre-operative bowel preparation

### Intra-operative data:

- Surgical skin preparation
- Surgical procedure- Including OPSC code
- Surgical duration
- Surgical classification (Clean to dirty)
- Surgeon status
- Surgical drain use
- Colonic perforation noted.

### Post-operative data

- Adverse events
- Infections: Defined by NNIS definitions
- Antibiotic consumption

## 7.7 Trial assessments

### Pre-operative assessment-Visit 1

- Medical history
- Antibiotic history

Colo-Pro Pilot

- Rectal swab
- QofL assessment

#### Intra-operative assessment-Visit 2

- Anaesthetic history
- Surgical history
- Antibiotic prophylaxis history
- Antibiotic blood concentrations

#### Post operative assessment-Visit 3, day 5 (approximately) post-operation, or day of discharge

- Medical history
- Antibiotic history
- Surgical site assessment: Where possible the surgical wound will be inspected and an SSI specific evaluation will be completed
- Infections assessed as per standard (HPA point prevalence survey) definitions

#### Post-operative assessments-Visit 4 (4A, 4B etc) (72 hourly post visit 3 while in-patient)

- Medical history
- Antibiotic history
- Surgical site assessment: Where possible the surgical wound will be inspected and an SSI specific evaluation will be completed
- Infections assessed as per standard (HPA point prevalence survey) definitions

#### Post-operative assessment-Visit 5, day 30-45 post-operation

- This will normally be completed by postal or telephone assessment though when possible the 30-day follow-up might be combined with a patients post-operative clinic follow-up.
- Surgical site infection questionnaire relating to outpatient SSIs
- Antibiotic history
- QofL questionnaire

### 7.8 Long term follow-up assessments

Duration of follow-up period: 1 year

Assessments to be carried out: Mortality assessments at 1 year via electronic health records.

Patients will be identified as 'lost to follow-up if they are unable to be contacted or declined further follow up.

Measures taken to obtain the information if visits or data collection time-points are missed: Medical notes will be reviewed where appropriate, questionnaires sent to patients or telephone interviews conducted.

### 7.9 Withdrawal criteria

The intervention is a single intervention, so withdrawal criteria are not expected to result from issues of being in the trial over a long period of time.

An acute event associated with the MP would therefore be the main medical reason for removal from the trial. An anticipated acute event e.g. recognition of allergy after enrolment, would also lead to removal from the trial. These cases should be discussed with a microbiologist to decide upon appropriate antibiotic prophylaxis if the surgical procedure is performed as planned. A microbiologist will want to know how much antibiotic has been administered prior to the allergy being recognised, and the expected duration of the procedure.

If withdrawn in this setting the participant would be included in the trial assessments as part of obtaining a complete data set for an intention to treat analysis.

Documentation to be completed on subject withdrawal (including recording reasons for withdrawal and any follow-up information collected with timing).

Withdrawn subjects are not to be replaced

### 7.11 Storage and analysis of samples

Criteria for the collection, analysis, storage and destruction of biological samples

Rectal swab

- Testing location: Old Medical School, Leeds General Infirmary.
- Timings of testing: Pre-operative
- Shipping details: Clinical transport system
- Sample destruction: At the end of the laboratory studies have been completed, not expected to be > 1 year after date of the participant recruitment.
- Sample storage
  - o Conditions: 4 degrees Celsius +/- 5 degrees Celsius
  - o Duration: As sample destruction
  - o Location: as testing location
  - o Long term storage: None
- Laboratory manual: Available in the Old Medical School, Leeds General Infirmary

Blood samples for antibiotic drug concentrations

- Whole blood
- 6 ml
- Blood tube: Serum separator tube
- Testing location: Southmeads antimicrobial reference laboratory.

- Timings of testing: 4 samples taken intra-operatively. One sample will be collected at approximately 10 minutes after antibiotic infusion. One sample will be collected prior to closing the surgical wound. The other two samples will be taken after the surgery is approximately 1/3rd and 2/3rds complete. If a patient is re-dosed intra-operatively one of these two samples can be moved to be taken prior to the re-dosing.
- Shipping details: On ICE to Southmeads Antibiotic reference laboratory
- Sample destruction: As per Southmeads local guidelines (not more than 7 days of result)
- Sample storage
  - o Conditions: Freezer (-20 or -80 degrees)
  - o Duration: Until testing
  - o Location: Leeds and Southmeads
  - o Long term storage: None

Responsibilities of the trial site in regard to samples: The trial site to ensure that samples are appropriately labelled in accordance with the trial procedures to comply with the 1998 Data Protection Act. Biological samples collected from participants as part of this trial will be transported, stored, accessed and processed in accordance with national legislation relating to the use and storage of human tissue for research purposes and such activities shall at least meet the requirements as set out in the 2004 Human Tissue Act and the 2006 Human Tissue (Scotland) Act.

## 7.12 End of trial

The date of the last visit/data item of the last patient undergoing the trial is the trial end definition

The study PI will notify REC of the end of the trial.

## 8 TRIAL MEDICATION

### 8.1 Name and description of medicinal product

#### Comparators

The comparator regimen is:

Cefuroxime

- Each vial contains, as the active ingredient, cefuroxime sodium for injection 1578mg equivalent to 1500mg of cefuroxime respectively

Metronidazole

- Metronidazole 5 mg/ml Solution

#### Medicinal Products

Cefuroxime

Colo-Pro Pilot

- Each vial contains, as the active ingredient, cefuroxime sodium for injection 1578mg equivalent to 1500mg of cefuroxime respectively

Metronidazole

- Metronidazole 5 mg/ml Solution

Route of administration

- Intravenous

## 8.2 Legal status of the drug

Cefuroxime

- Licensed at 1.5g 8 hourly dosing and 3g 8 hourly (meningitis)
- Indication: No BNF indication for surgical prophylaxis, although BNF provides dosing information for Surgical prophylaxis, 1.5 g by intravenous injection up to 30 minutes before the procedure.

## 8.3 Summary of Product Characteristics (SmPC)

A Summary of Product Characteristics (SmPC) will be used in this trial.

Updated versions will be incorporated into the trial after submission to the study sponsor, the National Research Ethics Committee (as appropriate).

## 8.4 Drug storage and supply

- The MPs will be supplied from normal hospital stock.
- The drug should be stored as per manufacturers guidelines

## 8.5 Preparation and labelling of Medicinal Product

Preparation: Cefuroxime sodium will be diluted in water for injection. A dose of 1.5 grams will be diluted in 50ml's of water for injection. Infusion will be according to Table 6 Labelling of infusion will be with infusion volume, drug concentration and infusion rate.

Of note: The NHS Injectable Medicines Guide Group (2015) state that there is evidence of Y-site compatibility for atracurium and cefuroxime (in glucose 5%). This information is reflected in the Handbook of Injectable Drugs by Trissel (2015).

## 8.6 Dosage schedules

Comparator

- Cefuroxime 1.5g 4 hourly throughout surgery. First dose given pre-operatively.

Intervention

Version 3 10/10/2016

The MPs are to be administered to achieve a steady state blood concentration of free serum concentrations of 4xMIC90 for the duration of an operation, up to a total duration of 6 hours.

In the intervention group, if surgery lasts for more than 6 hours, the infusion will be stopped and the dosing regimen will revert to 4-hourly bolus dose.

Antibiotics will be administered initially with a loading dose, intravenously as is standard practice for antibiotic prophylaxis, in order that drug concentrations can be reliably achieved for the start of an operation.

After the loading dose drug will be administered by continuous intravenous infusion.

Timing of each dose: Loading dose will be within the hour before surgery, with initiation of the continuous infusion before surgery.

To achieve this, the following calculations will be used to determine the bolus dose and the hourly dose.

$$\text{Loading dose (mg)} = C_{\text{peak}}(\text{mg/L}) \times V_d(\text{L/kg}) \times \text{weight (kg)}$$

$$\text{Maintenance infusion rate (mg/h)} = C_{\text{ss}} (\text{mg/L}) \times \text{Cl}_{\text{total}} (\text{L/h})$$

$$\text{Maintenance infusion rate in renal impairment (mg/h)}$$

$$= \text{maintenance infusion rate} \times (\text{CrCl}/100)$$

$$\text{Cl}_{\text{total}} (\text{L/h}) = K_e(h-1) \times V_d(\text{L/kg}) \times \text{weight (kg)}$$

$$K_e(h-1) = 0.693/t_{1/2}$$

$$C_{\text{peak}} = \text{target peak concentration}$$

$$V_d = \text{volume of distribution}$$

$$C_{\text{ss}} = \text{target mean steady state concentration}$$

$$\text{Cl}_{\text{total}} = \text{total body clearance}$$

$$K_e = \text{elimination rate constant}$$

$$t_{1/2} = \text{half life}$$

$$\text{CrCl} = \text{Creatinine clearance}$$

Cefuroxime dosing recommendations are provided below, Table 7.

Table 7: Cefuroxime dosing guidelines

Weight (kg)	Loading dose (mg)	Continuous infusion dose: Based on creatinine clearance (ml/min)					
		40-50	50-60	60-70	70-80	80-90	>90
30-40	617	128	157	185	214	242	285
40-50	793	165	202	238	275	312	367
50-60	970	202	246	291	336	381	448

60-70	1146	238	291	344	397	450	529
70-80	1322	275	336	397	458	519	611
80-90	1499	312	381	450	519	589	692
90-100	1675	348	426	503	580	658	774
100-110	1851	385	470	556	641	727	855

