It is not known how MICs relate to treatment outcome when using antibiotics for surgical prophylaxis. Expert publications have suggested that the time during the operation that the free (non protein bound) serum drug level is above the MIC is most likely to be predictive of treatment success (Moine 2013). By using clinical data on drug levels we can compare serum drug levels achieved throughout an operation in patients receiving standard doses of antibiotics to the antibiotic susceptibility of Enterobacteriaceae. A summary measure of Enterobacteriaceae susceptibility is the MIC90. The MIC90 is the MIC value which includes 90% of a bacterial population. For the data provided in Table 1 the MIC90 is 16mg/L. These data suggest that treatment doses of antibiotics commonly used an antibiotic prophylaxis for surgery, e.g. cefuroxime (1.5g), does not reach blood levels which would inhibit the growth of 90% of bacteria for much beyond one hour of an operation (Table 2). These data should also be considered in relation to the variation in drug levels seen in a population of patients. In pharmacological models which take account of this variation, in patients with normal renal function, less than 40% of patients are predicted to have free serum drug levels of 8mg/l at 4 hours of surgery (Asín-Prieto 2015).

Table 2: Known and estimated cefuroxime serum drug concentrations after intravenous administration in relation to *E. coli* MIC90.

Drug		Drug concentration at 1 hour time intervals (mg/L) after a single intravenous dose				Reference
		1hr	2hr	3hr	4hr	
Cefuroxime 1.5g	Free drug: 50% of total drug	21.5	12.15	7.8	4	Estimated from Kucers' 2010
Cefuroxime MIC90 (mg/L)		16				

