### **Brief description of proposed study**

We propose to randomise patients due to undergo colorectal surgery to standard antibiotic prophylaxis or an interventional antibiotic prophylaxis regimen and assess surgical site infection (SSI) rates. Standard antibiotic prophylaxis is a pre-operative injection of cefuroxime, repeated every 4 hours. The intervention regimen is a loading dose of cefuroxime followed by a continuous infusion of cefuroxime until the end of surgery. The intervention regimen dosing will be calculated using a patient's renal function. The intervention regimen will target a free serum drug concentration of 64mg/L. This serum level is 4x the MIC90 for colonising Enterobacteriaceae. The rationale for this dosing regimen is summarised below. The primary objective of the study is to reduce by 50% the rate of surgical site infections after colorectal surgery.

The rationale for this study design is based on the following rationale. An expert assessment is that  $ft > MIC$  is the measure most likely to be applicable to prophylaxis (Moine 2013). But as shown in table 2, this measure is not achieved by standard prophylaxis regimens. Neither do clinical data suggest this target achieves optimal prophylaxis. Therefore there is an opportunity to optimise antibiotic prophylaxis dosing. As the exposure response-relationship (pharmacodynamic target) is unknown we could either complete a number of studies exploring different relationships, or compare standard treatment to a single regimen which included a number of exposure-response relationships. The two most common exposure-response relationships are the CMAX/MIC ratio and the  $ft > MIC$ . And it has been reported that killing, as opposed to inhibition used in MIC values, is optimised by achieving 4 times an MIC value (Macgowan). An antibiotic prophylaxis regimen which achieved drug concentrations of 4xMIC for the duration of surgery would therefore achieves a high CMAX/MIC ratio, high  $T > MIC$ , and optimise bacterial killing. Therefore, standard dose antibiotic prophylaxis will be compared against a PD target dosed antibiotic prophylaxis regimen. The PD target will be a free serum antibiotic concentration of 4xMIC90 for Enterobacteriaceae against cefuroxime. Bolus-Continuous infusion of antibiotic prophylaxis will ensure there is continuous targeting of this drug level throughout the operation.

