## **2 RATIONALE**

**Research question:** Does pharmacodynamic target (4x MIC90 free serum concentration) based continuous antibiotic dosing of antibiotic prophylaxis reduce the rate of surgical site infection after colorectal surgery when compared against standard antibiotic prophylaxis dosing regimens.

**Research hypothesis:** Pharmacodynamic target (4x MIC90 free serum concentration) based continuous antibiotic dosing of antibiotic prophylaxis reduces the rate of surgical site infections after colorectal surgery by 50% when compared against standard antibiotic prophylaxis dosing regimens.

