### Why closely related questions are not being answered

#### Weight based dosing/intra-operative re-dosing.

The CDC systematic review on the prevention of surgical site infections identified 10 key questions after consultation with expert sources. Five of these questions were related to antibiotic prophylaxis, three were answered with a recommendation, but two questions received no recommendation and were identified as an unresolved issue. These two questions relate to:

- 1- The safety and effectiveness of weight-adjusted dosing of parenteral prophylactic antimicrobial agents for the prevention of surgical site infection.
- 2- The safety and effectiveness of intraoperative redosing of parenteral prophylactic antimicrobial agents for the prevention of surgical site infection.

Both these questions are essentially asking if dosing of antibiotic prophylaxis can be optimised. The Colo-Pro study will address both these questions in a single study of optimised dosing of antibiotic prophylaxis. PK analysis has shown that weight is not an important variable in an optimised regimen, but renal function is. PD target dosing includes renal function within the dose calculation, which PK

analysis suggests is more important than weight, and the continuous infusion addresses the aim of re-dosing i.e. maintaining “therapeutic” drug levels through the operation.

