### Justification for the dosage regimen and treatment duration

Antibiotic prophylaxis at treatment doses is the most effective intervention for the prevention of SSIs. Despite this effective intervention a significant minority of patients, >10%, still suffer SSIs. Therefore, if it is possible to improve the efficacy of prophylaxis it is likely, given the limited benefits of other interventions aimed at reducing SSI rates, that this intervention would offer the most rewards in terms of reducing SSIs. To improve the efficacy of an antibiotic intervention it would be normal practice to design a dosing regimen using the known exposure-response relationship. An exposure-response relationship would define the most effective dosing regimen. Different exposure-response relationships have been identified in the treatment of infections. For example, aminoglycoside dosing is optimised by getting a high ratio of peak drug concentration/MIC. For beta-lactams the time the serum level is above the MIC is important. The exposure-response for antibiotics used for prophylaxis is unknown.

We have therefore decided to investigate if a pharmacodynamic (PD) target based dosing approach, with a single target that covers a number of different exposure-response relationships, is more effective than standard antibiotic dosing regimens. The use of a PD target, as opposed to simply giving higher doses, means that we address issues highlighted as being important. These include obesity and the need to maintain antibiotic drug levels throughout the duration of surgery. A PD target of a free serum drug concentration of 4 x MIC 90 value has been chosen as up to this level bacterial killing is reported to increase (MacGowan 2011). This level equates to 64mg/L for and cefuroxime, which is below a level of 100mg/L. It has been suggested that a level of <100mg/L is a safe beta-lactam target to aim for (Moriyama 2010). This level will potentially increase the killing of bacteria including those that are resistant (MIC>8mg/L). The PD target chosen, 4xMIC90, therefore addresses concerns that antibiotic resistance is impacting on the efficacy on standard dosing of antibiotic prophylaxis.

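### Section 8.6 promises free cefuroxime of 4xMIC90 (64 mg/L), but its formulas have no free-fraction step, and on the protocol's own Table 2 typical Table 7 doses give about half that

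*Combined protocol and SAP*

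**What the plan says.** The target is stated as free drug throughout. Section 1 (brief description of the study) says: "The intervention regimen will target a free serum drug concentration of 64mg/L". Section 2 (justification for the dosage regimen) says: "A PD target of a free serum drug concentration of 4 x MIC 90 value has been chosen". Section 8.6 says the products are "administered to achieve a steady state blood concentration of free serum concentrations of 4xMIC90". The hypothesis in section 2 carries the same label: "Pharmacodynamic target (4x MIC90 free serum concentration) based continuous antibiotic dosing of antibiotic prophylaxis reduces the rate of surgical site infections". So do the objectives in sections 3.1 and 3.2 and the full-study hypothesis in section 10.1.

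Section 8.6 sets the loading dose as Cpeak x Vd x weight and the infusion rate as Css x Ke x Vd x weight, with a CrCl/100 factor in renal impairment and Ke = 0.693/half-life. Cpeak and Css are described only as target concentrations. No values are printed for Cpeak, Css or Vd, and no free fraction appears.

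Table 2 in section 1 gives free levels after 1.5 g on the basis "Free drug: 50% of total drug". The control regimen in section 8.6 is "Cefuroxime 1.5g 4 hourly throughout surgery. First dose given pre-operatively".

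**The concern.** At 50% free, 64 mg/L free requires 128 mg/L total. Volume and clearance formulas of the kind in section 8.6 normally work on total drug. If 64 was entered without conversion, the doses aim at 32 mg/L free, or 2xMIC90, and the target is overstated by a factor of two.

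What is at stake is the name of the exposure being tested. A positive or a null result would be credited to 4xMIC90 free, and the full study would inherit that label. Section 1 also rests its case for a high peak/MIC ratio on the premise of "An antibiotic prophylaxis regimen which achieved drug concentrations of 4xMIC for the duration of surgery". That case weakens if the opening dose is smaller than the comparator's.

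**Working it through.** **Inputs.** MIC90 16 mg/L, free fraction 0.5, and free levels 21.5, 12.15, 7.8 and 4 mg/L at 1-4 h after 1.5 g (section 1, Table 2); half-life 1.5 h (section 2.1), so Ke = 0.693/1.5 = 0.462 per h; doses from Table 7; weight limits 30-110 kg (section 6.2).

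**Step 1: reproduce Table 7.** Use band-midpoint weight, midpoint CrCl/100 (1.0 for >90) and C x Vd = 17.63 mg/kg.
- 70-80 kg: load 17.63 x 75 = 1322 mg; rate 1322 x 0.462 = 611 mg/h.
- 100-110 kg: load 17.63 x 105 = 1851 mg; rate 1851 x 0.462 = 855 mg/h.
- 30-40 kg, CrCl 40-50: 17.63 x 35 x 0.462 x 0.45 = 128 mg/h.

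All 56 cells agree within 0.52 mg, so Cpeak equals Css and the half-life used was 1.5 h.

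**Step 2: kinetics from Table 2.** Total = free/0.5, one compartment, bolus input, V = 1500/C0 and CL = k x V.

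| Reading of Table 2 | k (per h) | Total C0 (mg/L) | V (L) | CL (L/h) |
|---|---|---|---|---|
| A: log-linear fit | 0.549 | 75 | 20.0 | 11.0 |
| B: 1.5 h half-life through the 1 h value | 0.462 | 68 | 22.0 | 10.2 |
| C: 1.5 h half-life, all four points | 0.462 | 60 | 24.9 | 11.5 |

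**Step 3: which concentration was entered?**
- 64 mg/L total: Vd = 17.63/64 = 0.275 L/kg, which matches Table 2 at a body weight of 73-90 kg.
- 128 mg/L total (64 free): Vd = 17.63/128 = 0.138 L/kg, which matches Table 2 only at 145-181 kg, beyond the 110 kg limit.

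**Step 4: free levels from the printed doses.** Free peak = 0.5 x load/V; free steady state = 0.5 x rate/CL.
- 70-80 kg, CrCl >90 (1322 mg, 611 mg/h), reference weight 75 kg: A 33.0 peak and 27.8 steady state; B 30.1 for both; C 26.6 for both. That is 27-33 mg/L, or 1.7-2.1xMIC90. With per-kg and CrCl scaling, other cells give nearly the same at their midpoints.
- Largest cells (1851 mg, 855 mg/h) in a Table 2 subject, without weight scaling: A 46.2 and 38.9; B 42.1 for both; C 37.2 for both.
- Dose such a subject would need for 128 mg/L total: 2563-3183 mg load and 1300-1471 mg/h.

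**Step 5: sensitivity.** Table 2 gives no weight or renal function, so both are assumptions.
- Reference weight 60-90 kg: 21-40 mg/L free; 110 kg: 39-48 mg/L.
- Reference CrCl 80 to 120, steady state: 21-36 mg/L at 75 kg; 31-53 mg/L at 110 kg.
- Extreme corner: reference weight 110 kg and CrCl 120, with a patient at 30 kg and CrCl 40 receiving 128 mg/h. CL is the Table 2 value x 30/110 x 40/120, giving free steady state of 64 (A), 69 (B) and 61 (C) mg/L. Under B, two other band-edge patients with the same reference also reach the target: 30 kg, CrCl 91, 285 mg/h (68 mg/L) and 60 kg, CrCl 40, 238 mg/h (64.5 mg/L).
- AUC understatement needed for 64 mg/L free: 855/128 = 6.68 L/h against CL 10.2-11.5, a factor of 1.52-1.72 for the largest rate; 611/128 = 4.77 L/h, a factor of 2.13-2.41 for the 70-80 kg rate.

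**Step 6: against the control bolus.** Loads for the five bands from 30 to 80 kg are 617, 793, 970, 1146 and 1322 mg, all below 1500 mg. The 80-90 kg load is 1499 mg; the two heavier bands exceed 1500 mg.

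**The case against.** The formulas were followed consistently, and a free-to-total conversion could have been made before Cpeak and Css were entered. With those values and Vd unprinted, the documents do not prove that 64 was used as total drug. This stands: the cause is an inference, although the volume needed for the alternative fits Table 2 poorly.

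Table 2 is four estimated textbook values starting at 1 h, extrapolated back with one compartment. Section 2.1 remarks that a bolus takes levels past 64 mg/L. If that means free drug after 1.5 g, V must be below 1500 x 0.5/64 = 11.7 L, which matches 0.138 L/kg at about 85 kg. If it means total, V must be below 1500/64 = 23.4 L, which fits readings A and B but not C. The remark does not say which, so it settles nothing. It does make the loading-dose result less secure than the infusion result.

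Exposure will also be measured. Section 7.11 plans four intra-operative samples without restriction by arm, section 10.1 sizes the pilot on 60 patients with samples, and the exposure-response objective in section 3.2 covers both arms. That helps before a full study, but it does not correct the label. Table 5's drug-level row covers standard dosing only, and sections 10.3.2 and 10.3.3 name only comparisons of proportions.

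A reader might infer that no Table 7 dose can reach 64 mg/L free. The corner cases in Step 5 rule out so absolute a statement. A reader might also infer that most patients receive a load no larger than the control bolus. The documents give no weight distribution, and the intervention infusion also starts before surgery, so only the band-by-band comparison is supported.

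**Conclusion.** Wrong as written. The regimen very probably does not deliver the free exposure claimed for it. The best estimate is about 27-33 mg/L free, roughly 2xMIC90 rather than 4xMIC90, with 37-46 mg/L for a Table 2 subject given the largest doses. This rests on 50% free, one-compartment linear kinetics, Table 2 as printed, a 75 kg reference weight for the first range and a CrCl factor of 1.0. The direction is robust across ordinary assumptions; the size is uncertain.

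Severity is below must-fix. It would be tempting to conclude that the trial is compromised or unsafe, but neither follows. The randomised comparison of the two regimens on infection is unaffected, and the discrepancy runs toward lower exposure. What needs correcting is the attribution of the result to a stated drug level.

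**What to change.** 1. Check and print the Cpeak, Css, Vd and free fraction behind Table 7, stating whether each concentration is free or total.
2. If 64 mg/L was total, keep the doses and restate the target in sections 1, 2, 3, 8.6 and 10.1 as 64 mg/L total, nominally 32 mg/L free or about 2xMIC90. If not, reconcile the printed values with Table 2.
3. Pre-specify a descriptive summary of measured free levels in the intervention arm: the proportion at or above 16, 32 and 64 mg/L at each planned sample in section 7.11.

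If the target is restated, the cost is a text amendment and one table from samples already planned, with doses, randomisation and sample size unchanged. The downside is that the stated exposure becomes less favourable.

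Doubling the doses to keep 64 mg/L free is a different decision for the sponsor. The 70-80 kg load would become 2644 mg, above the 2332 mg maximum in section 8.6. Total levels would be about 128 mg/L, against the 100 mg/L limit cited in section 2 (free or total not stated). That would need a new safety case.
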